7.2 Secondary Outcome Measures

Feasibility and Acceptability

Recruitment feasibility measures documented by study staff include the number of potential participants screened, number eligible, and number enrolled out of those eligible. Study retention will be defined as the proportion completing the end of intervention survey and a UDS. We will use the 13-item Social Media Usability scale (Lund, 2001) to assess participants' satisfaction with the intervention including perceived usefulness, ease of use, and willingness to recommend the intervention to others. The total score is the mean of all 13 items, with a potential range of 1 (low) - 5 (high) satisfaction, with higher scores indicating greater acceptability. We will also ask open-ended questions for feedback on any technical issues that occurred and suggested modifications to the prototype. For intervention engagement assessment, study staff will extract data weekly from the Facebook application programming interface (Facebook, 2020) using an extraction program based on a Python module (<https://pypi.org/project/facebook-scrapers/>) which we have utilized in prior work (Sinicrope et al., 2022). Standard engagement metrics for social media health promotion interventions (Pagato et al, 2016) include Facebook analytics of the number of *posts* 'seen by' group members, reactions (i.e., "like", "love", "care", "haha", "wow", "sad", and "angry"), and comments. Engagement *by participant* includes the number of comments, reactions, responses to a Facebook poll or other activities, attendance at live events (e.g., guest speakers) and posts initiated (i.e., participant created a post with text, image, and/or video). A total engagement count will be calculated from these metrics. The text of participant-generated posts and comments will be exported into an excel spreadsheet for analysis of content. Unlike many web-based platforms, Facebook analytics for private groups do not provide time spent on the Facebook page.

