10.2.2. Content Library and Intervention Moderator Guidelines

The Facebook intervention will have a three-month duration consistent with other addiction social media intervention platforms (Meacham et al., 2021; Ramo et al., 2015; Sinicrope et al., 2019). Content (moderator postings) will be refined based on results from the qualitative interviews. We will develop a content library (digital and written) similar to a conventional treatment manual for use by the moderators (Pagoto et al., 2016). It will contain at least 30 moderator postings. Moderators will post once every 1-2 days for the three-month duration; postings will be repeated each of the three months. Content for moderator postings will consist of images, audio, and video combined with text designed to provide information and stimulate participant discussion. The postings have been refined based on the feedback from the Phase 1 qualitative interviews and CAC feedback. Some refinements included keeping posts focused on one topic, avoiding overuse. Meta-themes derived from interviews that will be addressed in the group include keeping the group a positive experience for the participants, encouraging the participants to build a toolkit of ways to deal with stress using MBRP and SMART principles, keeping the language and topics in the group authentic and relatable to the participants, and incorporating exercises or local resources for the participants to take action after viewing posts. The moderator posts will be organized by topic, and each posting will include sample text the moderators could add to initiate discussion or modify according to current group conversations. The content library will also include (1) welcome posts, group description, (2) options for Facebook covers, (3) moderator guidelines for handling challenging conversations and posting of inappropriate posts or misinformation (e.g., deleting unrelated or false posts), (4) closing posts including additional places to connect to resources after the group ends. Based on feedback from Phase 1 participants, some specific types of postings will include personal stories from AIAN women in long-term recovery, coping mechanisms provided after introducing topics such as cravings and triggers, and Facebook live event to host a guest speaker who is knowledgeable of AIAN culture and/or opioid recovery. Participant information will not be disclosed to the guest speaker, but incidental occurrences may occur. To reduce the likelihood of these occurrences, we will tell participants in the consent form and a script in the content library to not share personal information so their identity and PHI can remain protected. We will incorporate artwork from Native artists as much as possible, also consistent with Phase 1 feedback. All data collection and study accrual for Phase 1 is complete.

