10.3.5. Study Intervention Administration

The Facebook intervention was described above in **Sections 10.1 and 10.2**. Participants will receive a welcome message when they join the group and a closing message when the group ends. The intervention will be accessible for a 30-day period. Participation in the intervention is entirely virtual and asynchronous, and available 24 hours a day/7 days a week so they can comment, react, and click on posts/links on their own time. The moderators will post one selection from the intervention content library once every 1-2 days and prompt group discussions as needed. Within the 30-day period, we may host up to 2 live guest speaker events. The guest speakers would be either a member of our research team that would present on a topic relevant to our content library posts or Native experts/Elders who are knowledgeable in opioid recovery and who are well-known and respected in the community.

Moderators will check in with the group every 1-2 days to interact with the participants, monitor adherence to group guidelines, and take actions such as removing inappropriate postings and misinformation if necessary.

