10.3.6. Study Intervention Adherence

Data will be extracted weekly from the Facebook application programming interface (Facebook, 2020) as described in **Section 10.3.9**. Intervention adherence will be operationalized as the level of engagement with the intervention and assessed with objective data obtained from Facebook analytics. This includes, for each of the 10 participants in the sample, Facebook group participation through number of comments, postings, reactions; attendance at live Facebook events (e.g., guest speakers), and responding to polls or other activities. These metrics will be summed to create a total engagement count. Unlike many web-based platforms, Facebook analytics for private groups do not provide time spent on the Facebook page.

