The qualitative findings will be discussed with the CAC who will guide us in the interpretation and integration of findings and resolving any discrepancies in themes for the AIAN women and stakeholder groups. In the LI's formative work to develop a social media intervention for nicotine use among Alaskan AIAN adults (Merculieff et al., 2021), differences were not found between AIAN smokers or community stakeholders in the acceptability of content (moderator postings) based on cultural relevance or perceived effectiveness. In addition to the feedback on the moderator postings, we expect the interested parties will provide unique information on how the intervention can best be promoted to engage AIAN women to participate in the study as well as factors in designing the intervention that would make the intervention appealing for sustained use within AIAN healthcare and community settings.

17.3.1.2 Phase 3

Survey: The Follow-up Survey contains four open-ended questions assessing the participant's experiences with the intervention, their recommendations for improving the intervention, and their thoughts on using the Facebook group as a way to learn how to mentor other AIAN women who are engaging in illicit opioid use to start their recovery. The text of survey responses will be entered into an Excel spread sheet for analysis. Analyses will generally follow the procedures described for Phase 1. Content analysis (Krippendorff, 2018) supplemented with QSR NVivo software version 10 (Doncaster, Victoria, Australia) will be used to generate response themes in the data for each of the three survey items. Coded data will be examined for any patterns in themes by age group, and substance use.

Facebook intervention group comments and postings: The text of participant-generated posts and comments will be exported into an excel spreadsheet for analysis of content. We will identify common themes of response in the data using content analysis (Krippendorff, 2018) supplemented with QSR NVivo software version 10 (Doncaster, Victoria, Australia). Analyses will generally follow the procedures described for Phase 1. We will summarize the major themes, and the frequency of topics discussed in participant comments and postings will be displayed graphically.

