19.9 Data Quality Assurance

The Manual of Operations will be developed by the Program Coordinator. We will use the same coordination, communication and quality control procedures successfully utilized in our previous work. Study staff will be trained using SOPs and the quality control of the data (accuracy and completeness of data) will be monitored monthly by the study statistician. The quality of the data (data checks) including missing data and presence and frequency of outliers. The site study team will meet weekly discuss progress and problem solve issues related to recruitment and data collection.

The interviewers for Phase 1 will be trained and certified by Dr. █. She will listen to the audio-recordings of the first four interviews conducted and provide feedback to the interviewers. She will listen to the audiotapes for another set of four interviews at the half-way point (after 15 are completed).

The intervention moderators will be trained as detailed in the procedures for Phase 2. A “refresher” training will occur every three months after the initial training. Dr. █ (Co-LI) and █ a consultant trainer, will review moderator-participant discussions every week after the Facebook group has been initiated and provide additional feedback to the moderators every two weeks.

The research team will develop written moderator guidelines for how often the moderator should log in, check-in and respond to comments/postings and other expectations for moderator

engagement. A potential concern about using social media for health interventions is that user postings may be of poor quality, for example, inconsistent with clinical practice guidelines or involve inappropriate or illegal activities. When participants enter the study, they will be informed about the policies for posting content and that any inappropriate postings will be removed. The moderator will be trained to handle inappropriate or misinformation, and to direct information content toward evidence-based information exchange and social support.

All study staff and volunteers will be required to complete and pass the CITI HIPPA/confidentiality course prior to any subject contact.

DRAFT

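### Moderators may remove posts at 1-2 day check-ins while data are extracted weekly, and no step records a post first, so removed content may be missing from the engagement count and content analysis

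*Combined protocol and SAP*

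**What the plan says.** **Removal.** Section 10.3.5 sets the moderators' rhythm: "Moderators will check in with the group every 1-2 days to interact with the participants, monitor adherence to group guidelines", and in the same sentence they may "take actions such as removing inappropriate postings and misinformation if necessary". Section 10.2.2 says the content library will hold guidance on inappropriate posts and misinformation, with the example "e.g., deleting unrelated or false posts", so off-topic material is covered as well as harmful material. Section 19.9 says participants are told on entry that "any inappropriate postings will be removed".

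**Data capture.** Section 7.2 says "study staff will extract data weekly from the Facebook application programming interface". Sections 10.3.6 and 10.3.10 repeat the weekly interval. The extracted comments, reactions, posts and activity responses are summed, with live-event attendance, into a total engagement count for each participant. Engagement is a secondary outcome.

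**Use of the text.** Section 17.3.1.2 says "The text of participant-generated posts and comments will be exported into an excel spreadsheet for analysis of content", followed by a theme analysis and a graph of topic frequencies.

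**Scoring rule.** Section 17.3.2.2 analyses all 10 women and gives a count of zero to anyone who never engaged with the group.

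No section describes copying, logging or counting an item before it is removed, or says how a removed item enters the count.

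**The concern.** The two schedules do not match. An item written and taken down between two extractions can disappear before the data collection sees it, along with any comments and reactions attached to it if deletion removes those too.

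The loss would not be random. Content is removed because it is inappropriate, false or unrelated, so the topic frequencies would under-represent those kinds of posting. Section 4.3.1 acknowledges that what participants will post cannot be known beforehand, and Section 19.9 names poor-quality user postings as a potential concern. A beta-test that will shape the prototype for a pilot RCT is a natural place to describe how often this happens, yet no such summary is planned.

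The engagement count is exposed too. With 10 women, and engagement described by age group, substance use and relapse, one woman's missing items can shift a subgroup description. A woman whose only activity was a removed post would be scored zero, the value meant for women who never engaged.

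**Working it through.** The protocol gives no figure for lost posts, so there is nothing of its own to reproduce. The check is a timing calculation.

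**Inputs from the protocol**
- Check-in interval: 1-2 days (Section 10.3.5).
- Extraction interval: 7 days (Sections 7.2, 10.3.6, 10.3.10).
- Intervention length: 30 days (Section 10.3.5), which is four full weeks plus 2 days.

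**Assumptions not in the protocol**
- The extraction returns only content still live.
- No other copy is kept.
- Items are written at a random point in the week.
- The time an item stays up before removal is L days, varied below.

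**Formula.** An item that stays up L days (L < 7) is caught only if it was written in the L days before an extraction. The chance is L/7, or mean(L)/7 when L varies.

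**Results for a regular weekly schedule**

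| Removal pattern | Mean L (days) | Caught | Missed |
|---|---|---|---|
| First check, 1-day checks | 0.5 | 0.5/7 = 7.1% | 92.9% |
| First check, 2-day checks | 1.0 | 1/7 = 14.3% | 85.7% |
| Every item up the full 2 days (upper bound for removal within 2 days) | 2.0 | 2/7 = 28.6% | 71.4% |
| Second check, 1-day checks | 1.5 | 1.5/7 = 21.4% | 78.6% |
| Second check, 2-day checks | 3.0 | 3/7 = 42.9% | 57.1% |

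Most removed items are missed as long as mean L is below 7/2 = 3.5 days.

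**Effect of the 30-day window.** With extractions on days 7, 14, 21 and 28 only, the 2-day bound is 4 × 2/30 = 26.7% caught. An extra extraction on day 30 makes it 5 × 2/30 = 33.3% caught, 66.7% missed. So the 71% figure moves by a few points with the end-of-study arrangement.

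**Simulation.** Check gaps were drawn between 1 and 2 days over the 30-day window.
- Removal at the first check: 89.6% missed, or 87.0% with a day-30 extraction.
- Removal at the second check: 69.6% missed, or 63.3% with a day-30 extraction.

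**Would more frequent extraction help?** With daily extraction and removal at the first check, the chance of capture is the mean of min(L, 1), with L uniform from 0 to the check interval. That is 50% for 1-day checks and 75% for 2-day checks. A record made at the moment of deletion captures every removal by construction.

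**The case against.** The strongest reply is that the loss is inferred, not shown. A reader might conclude that most deleted posts never reach the data. The documents do not support that as a statement of fact, for three reasons:
- They do not say that the extraction program returns only live content.
- They set a check-in interval, not a removal deadline. Section 10.2.3 lets moderators describe an incident to the Elder consultant and take advice, which could delay removal.
- They do not say that no copy is kept. The moderator guidelines, Manual of Operations and SOP are separate documents and could already contain a log.

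All of this stands, and it is why the figures are conditional.

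A reader might also infer that problem content goes entirely unrecorded. That goes too far. The trainer's weekly review of discussions, consultation with the Elder, adverse event evaluation by moderators, direct messages from participants and the open-ended follow-up questions can all bring problems to the team. None of these is stated to feed the engagement count or the analysis of posted text, and the trainer review is itself weekly, so the narrower gap remains.

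The effect may also be negligible. The team's earlier Facebook beta-test of 10 people had one incident of content shared outside the group and no other confidentiality or boundary violations (Section 4.3.1). That report does not cover misinformation or off-topic posts, but it gives no reason to expect many removals. The engagement analysis is descriptive, with no test or success threshold.

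Finally, it is debatable whether removed posts should count as engagement, and keeping their text has a privacy cost. Both points stand and shape the fix.

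**Conclusion.** The protocol pairs removal at check-ins every 1-2 days with weekly extraction and states no step to preserve what is removed. If the extraction sees only live content, no copy is kept, and items come down within 2 days of being written, at least about 71% of removed items would be missing from the engagement count and content analysis (about 67% if there is also a day-30 extraction). Across the removal patterns tried on a regular weekly schedule, the share missed runs from 57% to 93%.

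These are shares of an unknown number of removals, which may be very small. The documents do not establish that any result would change. What holds is that any loss would be selective, that with 10 participants a single case could misclassify a woman as never engaged, and that a planned record would remove the problem. This is a low-cost improvement to make before the group opens, because deleted content may not be recoverable afterwards.

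**What to change.** Add a step to the moderator guidelines, with a cross-reference in Section 10.3.5. Before deleting an item, the moderator records:
- the date, the author's study ID, the type of item and the reason for removal;
- the number of attached comments and reactions, by study ID;
- the text, with identifying and third-party details taken out.

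Store the log under the existing confidentiality safeguards.

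In Section 17.3, add three lines:
- Report the number of removals and the reasons as a descriptive feasibility result.
- Include the de-identified text in the content analysis as a separate category.
- Show the total engagement count with and without logged items, so that a woman whose only activity was removed is not recorded as never having engaged, and readers can judge whether such items should count.

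If the guidelines already contain such a log, the cross-reference and the three analysis lines are enough.

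The cost is a minute or so of moderator time per removal and a small privacy burden from keeping a de-identified record of content judged unsuitable for the group.

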10.3.6. Study Intervention Adherence

Data will be extracted weekly from the Facebook application programming interface (Facebook, 2020) as described in **Section 10.3.9**. Intervention adherence will be operationalized as the level of engagement with the intervention and assessed with objective data obtained from Facebook analytics. This includes, for each of the 10 participants in the sample, Facebook group participation through number of comments, postings, reactions; attendance at live Facebook events (e.g., guest speakers), and responding to polls or other activities. These metrics will be summed to create a total engagement count. Unlike many web-based platforms, Facebook analytics for private groups do not provide time spent on the Facebook page.

10.3.7. Discontinuation of Study Intervention

If the subject never engages in the Facebook group or discontinues from the intervention but not from the study, remaining study procedures will be completed as indicated by the study protocol.

If a clinically significant finding is identified (including, but not limited to changes on the K6 scale from baseline) after enrollment, the investigator or qualified designee will determine if any change in participant management is needed. Any new clinically relevant finding will be reported as an adverse event (AE) if it meets the definition specified in Appendix A of the protocol. A plan is in place for clinical management of depression and other psychiatric symptoms or medical problems. The study staff will refer participants to the appropriate on-call physician or behavioral health clinician at the appropriate medical facility. The study staff will have a list of contacts as participant issues or concerns arise that need medical or psychiatric attention, or when other types of referral or assistance are needed. Individuals who report suicidal intent or other severe psychiatric symptoms or medical problems will be referred for treatment and followed throughout the study period. Continued participation with the study will be voluntary and in cooperation with the health care professional treating the subject's psychiatric or medical condition.

The study staff will be trained by [name], licensed clinical psychologist, and Dr. [REDACTED] [REDACTED], Mayo Clinic Board Certified Psychiatrist, to observe and monitor depression and psychiatric symptoms. They will be available to consult with the study staff as needed.

In the event a participant withdraws from the study or the LI decides to discontinue a participant due to an SAE, the participant will be monitored by the LI via ongoing status assessment until:

- (1) Resolution is reached (i.e., the problem requiring treatment has resolved or stabilized with no further changes expected)
- (2) The SAE is determined to be clearly unrelated to the study intervention
- (3) The SAE results in death.

10.3.8 Follow-Up

Assessments will be conducted at the end of the intervention with a six-week visit window for completion (King et al., 2020). The participants will complete a UDS and a Follow-up Survey (by phone or in-person at the UDS visit). Study staff will attempt to contact the participant up to three times to complete the assessments and additionally reach out to the participant's secondary contact as needed. If the participant cannot be contacted within the six-week visit window, they will be considered lost to follow-up. Participants will receive a \$ [REDACTED] cash card for completing the Follow-Up Survey. They will receive an additional \$ [REDACTED] [REDACTED] cash card for completing the in-person UDS as a thank you for their time and for any travel costs incurred.

Follow-up Survey measures will evaluate treatment satisfaction and user experience using the Social Media Usability scale as well as four open-ended questions. It will also ask for the participant's thoughts on the potential for the group to be used as a way to encourage women to start their recovery journey and whether the participant would be interested in a peer moderator role for a future Facebook group. The TLFB will be used to assess opioid, opiate, and fentanyl use and MOUD use for each day since the previous TLFB assessment conducted at screening. We will again collect information on other OUD treatments the participant completed within the 30 days during the intervention. Using the TLFB, we will again assess for other substance use including stimulant use such as methamphetamines, cocaine/crack and marijuana use. The UDS

will be conducted in-person and staff will follow the same procedures as described above for the screening visit.

The Follow-Up Survey will include the same items from WHOQOL SRPB as the Baseline Survey to assess any changes in how their spirituality affects their Quality of Life and the K6 scale to assess changes in psychiatric symptoms during their participation in the Facebook group. It will also ask how important the participant feels it would be for Facebook groups like the pilot group to address spirituality from 0=not at all important to 10=very important. The study staff will assess adverse events (AEs) and serious adverse events (SAEs) including self-reported trips to the emergency department (ED), hospitalizations, and overdoses since enrollment.

